11.3 Vital Signs and Physical Examinations

Vital signs, complete Physical Examinations (PE) and Focused PE will be performed according to the Schedule of Events, page 10.

A complete PE (review of all body systems) will be performed at screening and completion visits. At all other scheduled visits, a Focused (symptom-directed as well as mandatory pulmonary examination) PE will be performed as appropriate.

A complete PE includes a review of the following systems: head/neck/thyroid, eyes/ears/nose/throat, respiratory, cardiovascular, lymph nodes, abdomen, skin, musculoskeletal, and neurological. Breast, anorectal, and genital examinations will be performed only when medically indicated. After screening, any clinically significant abnormal findings in PE should be reported as AEs.

Vital signs include blood pressure (systolic and diastolic), temperature (oral or tympanic), pulse rate, oxygen saturation and respiratory rate. These will be assessed following a 5-minute rest (seated) and before any scheduled blood sample collection and Pulmonary Function Testing, but after ECG and questionnaires (see Section 9.1 for Timing of Assessments). At visits when study drug is taken at the site, vital sign assessments will be collected before dosing.

11.4 Electrocardiograms

Standard, digital 12-lead ECGs will be performed according to the Schedule of Events, page 10.

Sites will use their own ECG equipment. A window of ± 15 minutes will be permitted around the nominal times for all post-dose ECG assessments. Additional 12-lead ECGs should be performed at any other time if clinically indicated and such instances should be recorded in the proper unscheduled event e-CRF.

Performance of all ECGs must adhere to the following guidelines in order to minimize variability and consistent assessments of each patient from time point to time point.

- ECGs will be performed after the patient has been supine for at least 5 minutes;
- The ECG will be performed before any other procedures that may affect heart rate (HR; e.g. blood draws, including PK, see Section 9.1 for Timing of Assessments);
- The ECG will be performed before the morning dose of study drug during the Treatment Period.

A hard copy of the ECG will be printed and signed by the Investigator at the site. To ensure the safety of the patients, the Investigator or designee at the clinical site will compare all QT segment-corrected (QTc) measured after predose on Day 1 to the average of the predose measurements of QTc on Day 1. If the QTc is increased by >45msec from the average of the predose measurements on Day 1 or the absolute QTc value is >500msec for any scheduled ECG, two (2) additional ECGs will be performed within 10 minutes, at least 1 minute apart, to confirm the original measurement. If either of the QTc values from these repeated ECGs remains above the threshold value (>45msec from the average of the 3 predose values on Day 1 or >500msec), a single ECG must be repeated at least hourly until QTc values from 2 successive ECGs fall below the threshold value that triggered the repeat measurement. If the QTc value remains above the threshold value (>45 msec from the average of the 3 predose values on Day 1 or >500 msec) on repeated measurement or is noted on >2 occasions with no identified alternative etiology for the increased QTc study drug, then discontinuation from study drug treatment may be required after discussion with the Medical Monitor. Patients in whom treatment is discontinued for increased QTc should have their QTc monitored closely until it normalizes or returns to baseline.

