9.2.2 Baseline and First Dosing Visit (Visit 2, Day 1)

1. Eligible CF patients will be invited to the study site for the baseline procedures and first dosing. This visit must be within 28 days of screening otherwise all or a part of expired screening procedures will need to be repeated/updated (see Section 9.2.1.2);
2. Confirmation of continued eligibility by verification of the inclusion/exclusion criteria, review of the results of the screening safety laboratory tests including plasma retinol and retinol-binding protein, performance of baseline vital signs, urine pregnancy test for women, and focused physical examination;

3. Pulmonary function tests (FEV₁). The actual baseline FEV₁ value for the study will be the average of the screening's best value and the best value obtained during the baseline visit as long as the screening and baseline FEV₁ values are within 15% of each other. A higher difference in FEV₁ % predicted indicates a lack of acceptable pulmonary function stability and the patient should not be randomized on study;
4. Body weight, with BMI calculated;
5. At sites that participates in the bone density exploratory assessment, the first 24 patients who consent to the additional procedure of measuring bone density prior to and after the study treatment, will undergo their baseline assessment; being not exclusionary, this test may be scheduled within a few days of first dose but not after;
6. Baseline Quality of Life questionnaire will be filled out (CFQ-R);
7. At select sites participating in the investigation of the Matouk Disease Score, the Baseline Score will be determined;
8. Pre-dose blood sampling and urine collection for baseline safety laboratory tests, pregnancy test if applicable, plasma retinol and retinol-binding protein, lipidomic tests, ceramides, metabolipidomic tests, systemic bone formation/resorption markers, inflammation and oxidative stress markers;
9. All eligible patients will be stratified according to 1- Baseline FEV₁, 2- PEx number in the prior year, and 3- Co-administration of Kalydeco® (ivacaftor), Orkambi® (ivacaftor/lumacaftor), Symdeko® (ivacaftor/tezacaftor) or another commercially available CFTR modulator product, and equally allocated/randomized to either a daily dose of 300mg of LAU-7b, (as 3 x 100 mg oral hard gelatin capsules), or matching placebo.

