10. Randomized patients will receive their first dose of study treatment under supervision, under fed condition and will receive a 21-day supply of study treatment. Patients will be discharged after tolerability of the first dose has been observed (minimum one hour post-dose).

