12 STATISTICAL ANALYSIS

A statistical analysis plan (SAP) will provide details of the methods of analysis to address all study objectives. The SAP may be amended during the course of the study, but will be finalized before the cutoff date for any analysis.

Data summaries by treatment group will be presented. For continuous variables, data will be summarized with the number of patients, mean, standard deviation, median, and minimum and maximum values by treatment group. For categorical variables, data will be tabulated in frequency tables to display the number and proportion of patients for each category by treatment group. Baseline assessments for each outcome variable will be defined as the last measurement obtained before the first dose of study drug except the baseline FEV₁ which will be the average of the screening and baseline best values, to reduce variability. Statistical significance will be set at the 5% level.

Diligent efforts will be made to prevent missing data in the study. For example, patients who discontinue the study treatment early or initiate medication changes (including those prohibited by the protocol) should still be followed for all regularly scheduled visits for safety and relevant efficacy assessments, or for a minimum of a 1-month follow-up. A clear distinction should be made between treatment discontinuation and study withdrawal. Efficacy assessments occurring after treatment discontinuation should not be included in the per-protocol analysis.

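### The relative QTc safety trigger in Protocol 11.4 refers to three predose Day 1 ECGs that the plan never schedules

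*Protocol*

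**What the plan says.** Protocol 11.4 states that ECGs follow the Schedule of Events. It then asks the site to compare every QTc "measured after predose on Day 1 to the average of the predose measurements of QTc on Day 1". The trigger has two limbs:

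- **Relative:** "If the QTc is increased by >45msec from the average of the predose measurements on Day 1".
- **Absolute:** a QTc above 500 msec at any scheduled ECG.

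If either limb is met, two more ECGs are required within 10 minutes. If either repeat stays above the threshold, ECGs continue at least hourly until two in succession fall below it. A persistent or recurrent exceedance without another cause can lead to stopping study drug after discussion with the Medical Monitor. In the parts on repeats and on discontinuation, the relative reference is described as "the average of the 3 predose values on Day 1".

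The Schedule of Events (Protocol Section 2) marks the 12-lead ECG at Screening and on Days 21, 77, 161 and 189. The Baseline (Day 1) cell is empty, and SAP Table 1 has the same row.

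In the visit descriptions, Section 9.2.1 includes one ECG at screening. Section 9.2.2 lists for Day 1 the "performance of baseline vital signs, urine pregnancy test for women, and focused physical examination", spirometry, weight, questionnaires and samples. It ends with dosing ("Randomized patients will receive their first dose of study treatment under supervision") and has no ECG among its ten items.

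**The concern.** The rule needs a reference that the plan does not collect, and the reference that the plan does collect is not the one the rule names. A site following both parts of the protocol has nothing to subtract at Day 21 or later. It must skip the relative limb or choose its own substitute.

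The relative limb does work that the absolute limb cannot. Since 455 + 45 = 500, any patient whose reference QTc is below 455 msec reaches a 45 msec rise before reaching 500 msec. No criterion in Sections 8.1 and 8.2 restricts QTc at entry. For a rise above 45 msec that stays at or below 500 msec, the required repeats, the hourly ECGs and the Medical Monitor discussion would be lost. The comparison is made at each site on its own equipment, at roughly 35 to 40 centres, and Section 11.4 describes no central ECG reading that could supply the missing value.

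**Working it through.** **Step 1. Values required and values scheduled.**

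| Item | Source | Count |
|---|---|---|
| Predose Day 1 ECGs the rule averages | Protocol 11.4 | 3 |
| ECGs scheduled on Day 1 | Schedule of Events; SAP Table 1; Protocol 9.2.2 | 0 |
| Planned ECGs before first dose | Protocol 9.2.1 (screening) | 1 |
| Planned ECG visits after first dose | Schedule of Events; Protocol 9.2.5 and 9.2.6 | 4 (Days 21, 77, 161, 189) |

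The plan's figure of three predose values cannot be reproduced from its own schedule. A broken table does not explain the empty cell: the neighbouring Vital Signs row is marked at Baseline, both documents show the same pattern, and the Visit 2 text agrees.

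**Step 2. Reach.** At the planned minimum of 136 patients, with no dropout:

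- All post-dose ECG visits: 136 × 4 = 544.
- Days 21 and 77 only: 136 × 2 = 272.

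These are ECGs at which the limb cannot be applied, not expected events. The count is not a ceiling, because Section 12.1 plans for at least 136 to start dosing.

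**Step 3. Where stopping drug still matters.** Six 28-day cycles with 21 days on drug (Sections 9.4 and 9.5) give dosing on Days 1–21, 29–49, 57–77, 85–105, 113–133 and 141–161. Dosing days left, counting the visit day and using the windows in Section 9.2.5:

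- Day 21 visit: 1 + 5 × 21 = 106 on Day 21; 105 on Day 22.
- Day 77 visit: 1 + 3 × 21 = 64 on Day 77; 63 on Days 78–79.
- Day 161 visit: 1 on Day 161; 0 on Days 162–163.
- Day 189: 0.

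**Step 4. Price of a screening reference.** The documents give no QTc variance, so this step rests on assumptions. Let *w* be the tracing variance, *b* the between-day variance, and *d* the variance of drift from screening to Day 1.

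- Variance of the change with one screening tracing: 2*b* + 2*w* + *d*.
- Variance of the change with three same-day tracings: 2*b* + *w* + *w*/3 = 2*b* + 4*w*/3.
- SD ratio = √[(2*b* + 2*w* + *d*) / (2*b* + 4*w*/3)].

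| *b* | *d* | SD ratio |
|---|---|---|
| 0 | 0 | √1.5 = 1.22 |
| *w* | 0 | √1.2 = 1.10 |
| 0 | *w* | √2.25 = 1.50 |
| *w* | *w* | √1.5 = 1.22 |

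**Step 5. Price of the alternative.** Three Day 1 ECGs per patient: 136 × 3 = 408 additional tracings.

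**The case against.** The best defence is that a sensible site would use the screening tracing. Section 12 says "Baseline assessments for each outcome variable will be defined as the last measurement obtained before the first dose of study drug", which for ECG is the screening value. SAP 3.8 and 3.18 already take ECG change from screening. Another site might record the Day 1 tracings that Section 11.4 describes. On this view the result is uneven practice between sites rather than a rule nobody applies. That may well be what happens, but the Section 12 definition and the SAP govern analysis. Section 11.4 names a different reference four times, and neither document authorises a substitute. The Study Reference Manual was not available and could settle the matter either way.

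Other points stand in part:

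- **Remaining safeguards.** The absolute limb is intact. Section 11.4 also says "Additional 12-lead ECGs should be performed at any other time if clinically indicated", Section 11.1.2 requires clinically significant worsening to be reported as an adverse event, and Section 8.4 lets the investigator stop treatment. Discontinuation under the QTc rule is itself discretionary, and the readable text states no specific QT concern for fenretinide. This limits the seriousness.
- **The count of 544.** Half of these ECGs fall at Day 161 or Day 189, when little or no dosing remains. The figure of 272 is the more relevant one.
- **The SD ratios.** They cover four chosen cases. With no drift and larger between-day variance the ratio approaches 1.0; with larger drift it exceeds 1.5.
- **Timing.** SAP version 6.0 is dated September 2021. An amendment cannot bring about repeat ECGs at visits already past.
- **Leftover wording.** Section 11.4 also gives a time window for post-dose ECGs, although none is scheduled. This does not affect the trigger.

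**Conclusion.** The concern holds. As written, the relative limb of a per-patient safety rule has no input: it needs three Day 1 values and none is planned. It cannot be calculated at about 544 scheduled ECGs at the planned minimum enrolment without dropout. Of these, about 272 fall where 105–106 or 63–64 dosing days remain. This weakens monitoring for QTc rises above 45 msec that stay at or below 500 msec. It does not remove QTc monitoring, and it touches no efficacy result and no SAP ECG table. It should be fixed because the rule protects individual patients and the repair is small. The conclusion rests on the protocol and SAP as they stand, without the Study Reference Manual.

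**What to change.** In Section 11.4, replace all four references to the Day 1 predose average with the screening ECG, taking the latest one if the patient was rescreened. Reword the phrase that limits the comparison to ECGs after the Day 1 predose set so that it covers every ECG after the first dose. That is five phrases in one paragraph. The screening ECG is planned for every patient, so the rule also becomes usable at the remaining visits of patients already dosed.

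**Cost.** No new visit, procedure or data item. Section 16.2 treats clarifications of confusing wording as administrative, but this change redefines a safety trigger. It is therefore probably a substantial amendment needing regulatory and IRB/IEC approval.

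**Downside.** The reference becomes a single tracing that can be up to 28 days old ("This visit must be within 28 days of screening"). The SD of the QTc change is then about 22% larger than with three tracings under equal, independent tracing error, and 10% to 50% larger over the cases shown. The confirmatory ECGs do not reduce error in the reference.

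**Alternative.** Add three predose Day 1 ECGs to the Schedule of Events and to Visit 2. This keeps the rule as designed, but it needs about 408 more ECGs at 136 patients and cannot help anyone already dosed.

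The SAP needs no change. Changing baseline to screening in the QT/QTc category of SAP 3.8 is optional and alters no result.

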3.8 Vital Signs/Physical Examination/ECG

Vital signs (blood pressure, temperature, heart rate, oxygen saturation and respiration rate) will be presented at each time point using descriptive statistics (mean, standard deviation, median, minimum, and maximum). Change from baseline values for each variable will also be presented by treatment group.

The number and percentage of patients that meet the abnormal criteria over time during the TEAE period will be presented by treatment group. The specific changes of interest are:

- Diastolic Blood Pressure ≤ 45 mmHg and decrease from baseline ≥ 10 mmHg, Diastolic Blood Pressure ≥ 110 mmHg and increase from baseline ≥ 10 mmHg;
- Systolic Blood Pressure ≥ 160 mmHg and increase from baseline ≥ 20 mmHg
- Temperature $\leq 35^{\circ}\text{C}$ and $\geq 38^{\circ}\text{C}$;
- Heart rate ≤ 50 bpm and decrease from baseline ≥ 20 bpm, heart rate ≥ 120 bpm and increase from baseline ≥ 20 bpm;
- Oxygen saturation values and respiratory rate determined by the Investigator to be clinically abnormal.

The number and percentage of subjects reporting normal and abnormal (NCS and CS) for physical exam at each visit will be described by treatment group.

For ECG measurements, a summary of raw values and change from screening values will be provided by treatment group for each scheduled time point for the following standard digital ECG

measurements: PR, QT, and QT corrected for heart rate (QTc) intervals, QRS duration, and HR. The number and percentage of patients with shift changes from screening (normal/missing, not clinically significant, and clinically significant according to overall ECG evaluation) to the worst ECG evaluation during the TEAE period will be tabulated by treatment group.

In addition, the number and percentage of patients will be tabulated by maximum on-treatment value of QT/QTc intervals, categorized as ≤ 500 msec and > 500 msec, as well as maximum on-treatment change from baseline value of QT/QTc intervals, categorized as > 30 msec.

No statistical analyses of vital signs or ECG data are planned.

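### The >45 msec QTc action rule in Protocol 11.4 is measured from Day 1 predose ECGs that the trial does not schedule

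*Protocol*

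**What the plan says.** Protocol 11.4 says that ECGs follow the Schedule of Events. It then tells the site to compare each later QTc with the Day 1 predose average and to act as follows: "If the QTc is increased by >45msec from the average of the predose measurements on Day 1 or the absolute QTc value is >500msec", two further ECGs are done within 10 minutes. If either repeat stays above the limit, ECGs continue at least hourly. If the value stays high on repeat measurement, or is seen on more than two occasions without another cause, "then discontinuation from study drug treatment may be required after discussion with the Medical Monitor". The Day 1 average is mentioned four times, twice in the form "from the average of the 3 predose values on Day 1".

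The same section sets a ±15 minute window "permitted around the nominal times for all post-dose ECG assessments", and also states: "The ECG will be performed before the morning dose of study drug during the Treatment Period".

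The Schedule of Events (Protocol section 2) and its copy in SAP Table 1 show a 12-lead ECG at Screening and Days 21, 77, 161 and 189. The Day 1 cell is empty. Protocol 9.2.1 lists one ECG at Screening. Protocol 9.2.2, for Day 1, lists "performance of baseline vital signs, urine pregnancy test for women, and focused physical examination" among its ten items, and no ECG.

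For analysis, Protocol 12 defines baseline as "defined as the last measurement obtained before the first dose of study drug". SAP 3.8 says that for ECGs "a summary of raw values and change from screening values will be provided by treatment group for each scheduled time point", and SAP 3.18 also refers ECG changes to screening.

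**The concern.** The rule in 11.4 is a safety instruction to sites that can end in stopping study drug. One of its two limbs is a change from a value that the visit schedule does not collect. A site following the protocol literally must either skip that limb or choose its own reference. With about 35 to 40 centres, each using its own ECG equipment, sites could choose differently.

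What would be lost is early detection of a QTc rise in patients who start at ordinary values. The exclusion criteria in Protocol 8.2 contain no QTc limit, so patients can enter at any starting value.

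**Working it through.** **1. Is the reference collected?** The plan gives no figure to reproduce, so this step sets the texts side by side.

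| Place | ECG on Day 1? |
|---|---|
| Protocol 11.4, the rule | Assumes three predose values |
| Protocol section 2, Schedule of Events | No |
| SAP Table 1 | No |
| Protocol 9.2.2, Day 1 visit list | No |
| SAP 3.8 and 3.18 | Not used; reference is screening |

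The rule needs three Day 1 ECGs and none is scheduled. One pre-treatment ECG is scheduled in total, at Screening. A table-reading error is unlikely: the Vital Signs row of the same table is marked at Day 1 and the ECG row is not. The visit list and the SAP agree with the empty cell. Protocol 11.4 allows extra ECGs when clinically indicated, which does not create a routine Day 1 triplicate.

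**2. When does the missing limb matter?** The two limits coincide at a reference of 500 − 45 = 455 msec. Below that, the change limb is reached first. If a site skips it, the rise needed before any limit is crossed is 500 minus the reference:

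| Reference QTc (msec) | Rise needed with the rule | Rise needed without the change limb |
|---|---|---|
| 400 | >45 | >100 |
| 420 | >45 | >80 |
| 440 | >45 | >60 |

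**3. What would a single screening ECG cost as the reference?** The documents give no QTc SD. Assume a within-patient single-ECG SD s of 7, 10 or 14 msec, normal errors, no drug effect, and 68 patients per arm (136/2). Count the four scheduled ECGs after first dose: Days 21, 77, 161 and 189.

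The quantity is P(max of four values − reference > 45), with each later value N(0, s²). The reference variance is s² for one ECG. For a mean of three it is s²[(1 − f) + f/3], where f is the share of variance that averages out across replicates, taken as 0.5 or 1. Numerical integration gives the chance of at least one trigger per patient; multiplying by 68 gives expected patients per arm.

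| s (msec) | Single reference | Mean of 3, f = 0.5 | Mean of 3, f = 1 |
|---|---|---|---|
| 7 | 0.001% (0.00) | <0.001% (0.00) | <0.001% (0.00) |
| 10 | 0.273% (0.19) | 0.096% (0.07) | 0.019% (0.01) |
| 14 | 3.83% (2.60) | 2.32% (1.58) | 1.05% (0.71) |

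At s = 14 the single reference adds 2.60 − 1.58 = 1.02 to 2.60 − 0.71 = 1.89 triggered patients per arm. At s = 10 it adds 0.12 to 0.18, and at s = 7 essentially none.

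**The case against.** The other side has several fair points.

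- **This is a procedural gap.** Protocol 12 and SAP 3.8 and 3.18 give the ECG tables a workable reference, and no statistical testing of ECGs is planned. That is correct. The fault lies only in the action rule.
- **The stopping consequence is narrow.** Cycle 6 dosing runs from Day 141 to Day 161 and treatment-period ECGs are predose, so at most one dose remains at Day 161 and none at Day 189. Stopping on a scheduled ECG matters mainly at Days 21 and 77, each just before a planned drug-free week. This stands. Counting only those two ECGs at SD 14 gives 1.46 chance triggers per arm with a single reference, against 0.36 to 0.84 with a mean of three. Repeat ECGs, however, can be triggered at all four visits.
- **The 100, 80 and 60 msec figures are a worst case.** They apply only if a site drops the limb. A sensible site would probably use the screening ECG. Clinically significant ECG worsening must also be recorded as an adverse event (Protocol 11.1.2), and the investigator may stop treatment on judgement (Protocol 8.4). These reduce the harm, but they give the rule no reference.
- **A noisier reference has costs beyond false triggers.** Repeat ECGs are compared with the same reference, so they cannot correct an error in it. Missed rises also increase slightly: for a true 60 msec rise at SD 14, one ECG fails to exceed 45 in about 22% of patients with a single reference, against 18 to 20% with a mean of three. Both points are fair and the cost is modest.
- **The Study Reference Manual may name a reference.** It was not available. Even if it does, the protocol would still contradict its own schedule.

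**Conclusion.** The concern holds. As written, the >45 msec limb of the QTc rule in Protocol 11.4 has no reference value, because it needs three Day 1 predose ECGs and the plan schedules none. This follows from the text alone and rests on no assumption.

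The practical weight is small. The >500 msec limb is intact, a screening ECG exists, stopping on a scheduled ECG matters mainly at two visits, and the primary FEV1 analysis is untouched. The comparison of single and triplicate references depends on the assumed SDs of 7 to 14 msec and serves only to price the repair. It is a worthwhile correction of low severity.

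**What to change.** In Protocol 11.4, replace all four mentions of the Day 1 predose average with the last ECG before the first dose, which on the schedule is the screening ECG. That wording also covers an unscheduled predose ECG on Day 1. It uses the reference that the SAP already uses and adds no procedure. The cost is a protocol wording change and the noisier single-ECG reference priced above.

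Two clerical edits can go with it: use the same reference wording for the ECG change categories in SAP 3.8 and Protocol 12.5 and 12.5.4, and remove or correct the post-dose window in 11.4. The >30 msec table cut can stay.

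The alternative is to add three predose ECGs on Day 1 to the Schedule and to 9.2.2. That keeps 11.4 as written and gives a more precise reference, but it adds procedures and cannot help patients already dosed.
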